The implementation of the Target Educational Campaign (TEC) will involve Correction Officers working at three jails: the Anna M. Kross Center (AMKC), the Rose M. Singer Center (RMSC), and the Robert N. Davoren Complex (RNDC), all located on Rikers Island in New York City. Correction Officers in these three jails will be approached to complete brief surveys. The study will need 540 completed surveys over the course of the three time points (180 surveys at each). Since identifying information is not being collected from the Correction Officers, it is possible that some of Correction Officers will participate more than once, meaning less than 540 Officers total will participate.

Recruitment Procedures

Recruitment of the study sample will take place in 3 jails on Rikers Island in New York City (NYC): Anna M. Kross Center (AMKC), Rose M. Singer Center (RMSC), and the Robert N. Davoren Complex (RNDC).

How and by whom will subjects be approached and/or recruited?

Correction Officers in these three jails will be exposed to the Targeted Educational Campaign (TEC). Correction Officers will be approached and recruited during roll call and in the staff canteen where they take their meal breaks, or at a time/location agreed upon by the Department of Correction, to complete brief surveys to assess engagement of Target C at three different times: pre-exposure, after 6 months, and after 12 months from the beginning of the TEC. [name] and [name], coordinated and supervised by [name] and [name], will approach Correction Officers briefly presenting the study and asking for completion of the survey.

In the event that social distancing guidelines pertaining COVID-19 prevent the research team for going to the jails to survey the Officers at the 6 and 12-month follow-up time periods, we will coordinate with our study partners to administer the anonymous survey. The Deputy Wardens and/or Captains at the jails will introduce the survey during the daily roll-call meetings, and they will distribute the participant information document and survey to each Officer for their review. The Deputy Wardens and Captains will tell the Officers that the survey is voluntary and anonymous, but if they wish to complete it, they can put their completed survey in a container in the Officer's canteen or other communal space.

Inclusion/Exclusion Criteria

Inclusion Criteria

1. Exposure to the Targeted Educational Campaign
2. Aged at least 21 years

Exclusion Criteria

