Any risk of perceived coercion will be addressed by fully informing participants that their decision to participate is voluntary and will not be reported to anyone outside of the research team. We (or in the event that we cannot distribute the surveys due to social distancing, the Deputy Wardens and Captains) will explain that their decision will in no way impact their relationship with their employer or others. Risks to confidentiality also will be minimized. Participants' names and other potential identifiers will not be included in the dataset and each participant will be assigned a unique ID number. Surveys will be made anonymous by using a unique code created by the participant, as in [name] prior survey-based research. For example, on the front page of the survey, respondents will be asked:

- What is the first letter of your middle name?
- What is the first letter of the street you live on?
- What is the last digit of the year you were born?
- What is the last two digits of your Social Security Number?

Doing so will create a unique identification code for each participant (e.g., JB223, TF189) to ensure anonymity, while allowing us to match any participants who complete a later survey (at 6 months or 12 months).

Method to Protect Confidentiality

We will collect some identifiable information that will be used for the purpose of determining basic eligibility criteria, and we will carefully protect such information. All information collected will be confidential and will not be disclosed outside of the research team. We will keep all records private and confidential to the extent permitted by law.

All initial screenings and interviews will be conducted in the same private interview rooms/spaces used by Correctional Health Services staff for meetings and counseling sessions. Consent forms with participants' signatures will be securely stored in a locked file cabinet in a locked research office in a secure building.

Subjects' name and other potential identifiers will not be included in the notes or dataset, and each participant in the study will be assigned a unique ID number. The only link between identifying information and the unique ID number will be the paper consent forms. Information pertaining to

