individual participants will only be released with their informed and written consent, except in unusual cases where withholding such information might pose a serious risk or danger to the participant or others. Publications and presentations will not report names, initials, or descriptors that could in any way violate confidentiality. These efforts to protect against potential risks are expected to be very effective, as they have been for our prior research.

Direct Benefits to Subjects

There may be no definite direct benefits to individual participants of the proposed study. Given the minimal risks and potential benefits of the proposed research to participants and the significant potential benefit of knowledge gained, there is no evidence that the risk-benefit ratio would suggest changes to the research plan at the present time.

Statistical Analysis Plan

The Targeted Educational Campaign (TEC) is designed to lead to referrals of detainees (previously not detected as having potential mental health concerns) to Correctional Health Services (CHS) by Correction Officers within 3 jails at NYC's Rikers Island. We expect that referral will occur via changes in scores on behavioral capability (knowledge/skills), expectations, and self-efficacy (among Correction Officers). Although this R34 feasibility study is meant to determine likely effect sizes rather than demonstrate statistical significance (which would be the goal of a subsequent, larger, multi-site study), using the data that we collect, we hypothesize that the number of referrals to CHS will be associated with: cumulative changes in Correction Officers' survey scores on behavioral capability, expectations, and self-efficacy.

Although survey participants who complete a short series of questions allow us to generate unique IDs that would be consistent across time, we expect that the number of surveys that matched from baseline to 6-months, from baseline to 12-months, and from 6-months to 12-months will be low. Therefore, rather than calculating changes in measurement scores as the primary outcome, each independent cohort (at each time point) will be considered to be a representative sample of the overall correction officer population over time, and we will use the measurement scores at 6-months as the primary outcome.

References

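### If the COVID-19 fallback is used, supervisors replace research staff as survey administrators at 6 and 12 months only, and the plan neither records nor handles that change of mode

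*Combined protocol and SAP*

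**What the plan says.** Recruitment Procedures sets three survey waves: before exposure, and 6 and 12 months into the campaign (TEC). By default, members of the research team "will approach Correction Officers briefly presenting the study and asking for completion of the survey". They do so at roll call, in the staff canteen, or elsewhere by agreement with the Department of Correction.

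The same section gives a fallback in case COVID-19 restrictions "prevent the research team for going to the jails to survey the Officers at the 6 and 12-month follow-up time periods". In that event "The Deputy Wardens and/or Captains at the jails will introduce the survey during the daily roll-call meetings". These supervisors, and not the research team, also hand every officer the information sheet and the form. Officers who choose to take part are told that "they can put their completed survey in a container in the Officer's canteen or other communal space". No fallback is given for the pre-exposure wave.

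Procedures for Minimizing Risks acknowledges the fallback. It says participants will be told that "their decision to participate is voluntary and will not be reported to anyone outside of the research team", and it has supervisors, where they distribute the survey, explain that the decision will not affect the officer's position with the employer.

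Study Procedures judges engagement of Target C by changes in mean scores for behavioral capability, expectations and self-efficacy, using pre-campaign and during-campaign surveys. The Statistical Analysis Plan expects few matched surveys and treats each wave as an independent, representative sample of officers. It then states that "we will use the measurement scores at 6-months as the primary outcome". It does not mention mode of administration.

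**The concern.** The analysis rests on the waves being comparable samples of the same workforce. If the fallback is used, the person who introduces and hands out the survey changes from a researcher to the officer's superior, and this can happen only after baseline. Officers may then answer differently, or different officers may answer. Expectations and self-efficacy are self-reported, and the campaign itself includes roll-call training, so a superior could be handing out its evaluation where part of it was delivered. A change in responder mix could also move the knowledge and skills score without any change in candour.

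Any such shift enters the 6-month mean and, through it, the difference from baseline. All three jails receive the campaign and no comparison jail is described, so nothing in the design would reveal the shift. The study is meant to supply likely effect sizes for a larger trial, so an undetected shift would carry forward into that trial's planning.

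**Working it through.** **Inputs from the documents.** 180 completed surveys at each of three waves (Description of Subject Population); three jails, all exposed; fallback named for 6 and 12 months only; 6 months primary; waves treated as independent. The plan's total reproduces: 3 × 180 = 540. No SD, alpha, power or target effect is given, so the basis of 180 cannot be tested.

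**Assumptions.** Outcome SD = 1, so results are in SD units; a two-sided 95% interval by normal approximation; 60 surveys per jail per wave (180 / 3). The size of the mode shift, d, is assumed over a range because the documents give none.

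**Step 1: can mode be separated from time?** Take a model with an intercept, two jail terms, two time terms and one mode term, which is 6 parameters, fitted to the 3 × 3 jail-by-wave cells.

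| Jails that switch | Rank (6 needed) | SE of 6-month change, adjusted for mode |
|---|---|---|
| None | no mode term needed | 0.105 SD |
| One, at 6 and 12 months | 6 | 0.124 SD |
| Two, at 6 and 12 months | 6 | 0.167 SD |
| All three, at 6 and 12 months | 5 | not estimable |
| All three, at 6 months only | 5 | not estimable |

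When all three switch, no analysis separates mode from the baseline-to-6-month change. When one or two switch, separation needs mode to be recorded and the time effect to be the same in every jail.

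**Step 2: precision of the contrast.** SE = √(2/180) = 0.1054 SD. The 95% half-width is 1.96 × 0.1054 = 0.207 SD.

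**Step 3: effect of an unmodelled shift, all jails switched.** Coverage = Φ(1.96 − d/SE) − Φ(−1.96 − d/SE). With no true change, the chance that the interval excludes zero is 1 minus that coverage.

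| Assumed d | d/SE | Coverage | Interval excludes zero, no true change |
|---|---|---|---|
| 0.1 SD | 0.95 | 84% | 16% |
| 0.2 SD | 1.90 | 52% | 48% |
| 0.3 SD | 2.85 | 19% | 81% |

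The formula is symmetric in d, so a downward shift of the same size does the same damage to coverage.

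**Step 4: partial switching, mode ignored.** With equal-sized jails, the bias is d/3 if one jail switches and 2d/3 if two do. For d = 0.3 SD that is 0.1 and 0.2 SD, which correspond to the first two rows of the table above.

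**The case against.** The strongest reply is that this is a fallback and not the plan. Research staff are the default at every wave, and nothing in the documents says the fallback was used. That stands. A reader might infer that the mode change necessarily coincides with the primary time point, or that it can never be separated from the campaign. The documents support neither. The change is conditional, and strict inseparability arises only if all three jails switch; no rule says they must switch together.

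A second reply is that the procedures differ less than they seem to. This also largely stands. Roll call and the canteen are already default venues, and the survey and its anonymity are unchanged. The default return route is not described, so the documents do not show that privacy is worse under the fallback; a container could be more private than handing the form to someone waiting. The clear change is who introduces and distributes the form. Supervisors must also give the reassurance about the employer. That addresses coercion but does not make the waves comparable.

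Third, a reader might infer that supervisor administration would inflate the apparent effect. That is plausible, but no passage gives a direction or a size. Favourable answering is less likely to affect knowledge items than attitudes, and the stigma scale is not one of the three Target C constructs.

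Fourth, the SAP names the 6-month score as primary, states no contrast with baseline, and aims at effect sizes rather than significance. The coverage figures therefore describe a comparison that the SAP does not write down. Study Procedures nevertheless judges engagement by change in means, so the 6-month score bears on engagement only when read against baseline.

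Finally, an uncontrolled pre-post difference cannot be attributed to the campaign even with constant mode. That is true and is the larger limitation. But secular trend is built into the design, whereas an unrecorded change of mode can be avoided or at least exposed.

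**Conclusion.** The point holds conditionally. If the fallback is triggered, a change of administrator falls only on the follow-up waves, including the primary one, and the plan has no means of recording it or dealing with it. With all three jails switched, mode and time are inseparable. With one or two switched, they can be separated only if mode is recorded and there is no jail-by-time interaction. The illustrative loss of coverage, to between 84% and 19%, rests on assumed shifts of 0.1 to 0.3 SD with all jails switched, 180 independent surveys per wave and a common SD. It shows how sensitive the contrast would be and does not predict bias. The problem adds to the secular-trend limitation of the design. A written fallback with no matching analysis rule merits an inexpensive correction, which should be in place before the fallback is needed.

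**What to change.** 1. Log administration mode (research team or supervisor) and setting by jail and wave, and link them to each survey, for instance by a pre-printed code. The survey form is not in the documents, so it may already carry jail or wave. If it does not, a log of mode by jail cannot be tied to anonymous forms.
2. Under the fallback, limit supervisors to announcing the survey. Use packets prepared by the research team, sealable return envelopes, and a locked box opened only by the research team. Use the same return method at every remaining wave, so that the safeguard does not itself create a further difference between them.
3. Add to the SAP: if any jail changes mode after baseline, the 6-month results are reported by jail and mode, with a sensitivity analysis restricted to jails whose mode did not change. If all jails changed, report the result under two-sided bounds on the mode shift, labelled as assumptions, and state that the difference cannot be attributed to the TEC alone.

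The cost is some envelopes and boxes, a code on the form and a short SAP paragraph. If mode does change, the reported effect may be wider or less favourable. With 60 surveys per jail per wave assumed, restriction to two unchanged jails gives a 95% half-width of 1.96 × √(2/120) = 0.253 SD, and to one jail 1.96 × √(2/60) = 0.358 SD, against 0.207 SD for all three. Sample size and campaign content do not change.

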Our intervention is critically informed by the TIPS study in Scandinavia, the largest experimental study of early detection to date. TIPS successfully reduced median DUP in FEP patients from 15 weeks to 4.5 using two core strategies: intensive, multi-media public information campaigns, and easy-access, low-threshold mobile early detection teams [16]. A wide body of literature attests to the pivotal role education campaigns can play in improving professional and public recognition of early warning signs and symptoms of many disorders [17]. TIPS developed a mass media campaign to both enhance the public’s knowledge of psychiatric disorders in general and early signs of psychosis in particular, and to reduce stigma associated with schizophrenia and psychiatry. Information was tailored to 3 target groups: the general public, general practitioners and healthcare workers, and teachers. Information was distributed systematically and repeatedly over several years. Notably, when a lack of funding interrupted the campaign for a period of time, the rate of referrals dropped (particularly from general practitioners) and DUP increased again, further showing the importance of information campaigns in reducing DUP [18]. The success of the TIPS campaign has led to efforts to replicate the approach in other places. In the US, the Specialized Treatment Early in Psychosis (STEP) clinic implemented the STEP-ED campaign that includes: public education, outreach to and academic detailing of professionals, and rapid access to the STEP clinic [19]. Our proposed intervention will take place in an urban jail setting rather than in the community; as such, it will focus on the same two interlocking strategies (TEC and SEET) used by TIPS to shorten DUP for people experiencing FEP, but tailored within the confines of the jail. The NYC jail system has over 55,000 admissions and roughly the same discharges each year, with high correctional staff turnover; a continuous and broad-reaching “Targeted Education Campaign” is essential to ensure the messaging works.

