The jail-based TEC (and our targets/mediators) are also heavily influenced by Social Cognitive Theory and its concepts of behavioral capabilities (knowledge and skills), self-efficacy, and expectations. Social Cognitive Theory, developed by Bandura [28-29], posits that behavior is underpinned by personal (cognitive, affective, and biological), behavioral, and environmental factors that interact and influence each other bidirectionally. As applied to the field of health promotion, Social Cognitive Theory specifies a core set of determinants, the mechanisms through which they work, and the optimal ways of translating them into health practices. Five determinants are central: (1) behavioral capabilities—or knowledge and skills about health risks and benefits—that create the preconditions for change; (2) perceived self-efficacy about one's ability to successfully perform tasks; (3) expectations about the outcomes of certain actions or health habits; (4) personal goals for change; and (5) perceived facilitators and barriers to change [30]. As described in more detail below, the TEC is an intervention that will target Correction Officers' knowledge about the early symptoms of psychosis, and how to make a referral to the CHS, their self-efficacy to detect symptoms of psychosis and make referrals, and their expectations about their ability to be successful in making that referral (and for referrals to result in beneficial outcomes). All aspects of the TEC will be designed to improve behavioral capabilities, expectations, and self-efficacy. That is, regardless of the media (e.g., poster, flyer, brief roll-call training for Correction Officers), all TEC materials will target very specific knowledge and skills, increase expectations about the benefits of the SEET and CSC/OnTrackNY, and increase self-efficacy about one's ability to make a referral. Messaging will be specific, straight-forward, as simple as possible, and repetitive, so that we can effectively improve knowledge/skills, expectations, and self-efficacy in a focused way. These changes will ultimately influence rates of identifying detainees with undetected FEP and referral to CHS. Social Cognitive Theory, as well as everyday experience, suggests that in order to successfully carry out a behavior, one must have the necessary knowledge/skills, the beliefs that what is expected to occur actually will occur, and the self-confidence to carry out that specific behavior. In targeting these mediators, our TEC will therefore have the greatest chances of generating referrals to the CHS (especially referrals of quietly psychotic young people who would have otherwise gone undetected and thus not referred to CHS).

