
Abundant evidence documents racial and ethnic disparities in access to mental health services [31-33]. While the underlying root causes of these disparities are complex—explained by patient-level, provider-level, and system-level factors—studies show that they persist even when controlling for differences in socioeconomics [32]. Racial and ethnic disparities also occur in pathways to care in FEP patients. Stigma remains a significant barrier to treatment and African Americans are more likely to experience negative routes to psychiatric care such as through the CJ system or involuntary hospitalizations [34-38]. Given that the population in the NYC jail system is 87% Black and Hispanic and that no specialized FEP treatment services currently exist within the jail system, our intervention has the potential to significantly improve treatment access for a population of young minorities with FEP who traditionally experience significant barriers to care.

Specific Aims and Hypotheses

Implement a Targeted Educational Campaign (TEC) within 3 jails at NYC's Rikers Island. The TEC is designed to lead to referrals of detainees (previously not detected as having potential mental health concerns) to Correctional Health Services (CHS) by Correction Officers. We expect that referral will occur via changes in scores on behavioral capability (knowledge/skills), expectations, and self-efficacy (among Correction Officers). Although this R34 feasibility study is meant to determine likely effect sizes rather than demonstrate statistical significance (which would be the goal of a subsequent, larger, multi-site study), using the data that we collect, we hypothesize that the number of referrals to CHS will be associated with: cumulative changes in Correction Officers' survey scores on behavioral capability, expectations, and self-efficacy.

Description of Subject Population

Specify subject population:

Correction Officers

Number of completers required to accomplish study aims:

540

Projected number of subjects who will be enrolled to obtain required number of completers:

540

Age range of subject population:

over 21

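### The referral hypothesis uses a count with no population denominator, so a change in jail census can hide or mimic a change in officer behaviour

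*Combined protocol and SAP*

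**What the plan says.** The first paragraph of the Statistical Analysis Plan, repeated in Specific Aims and Hypotheses, opens with the purpose of the campaign: to "lead to referrals of detainees (previously not detected as having potential mental health concerns) to Correctional Health Services (CHS) by Correction Officers". It closes with the hypothesis: "we hypothesize that the number of referrals to CHS will be associated with" cumulative changes in the officers' scores on the three Social Cognitive Theory constructs. The outcome is a number. No population denominator, counting window or data source is given for it.

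Background, Significance and Rationale puts the expected effect differently, in terms of rates: "These changes will ultimately influence rates of identifying detainees with undetected FEP and referral to CHS". The only population figure is system-wide: "The NYC jail system has over 55,000 admissions and roughly the same discharges each year". It is not broken down by jail or period, and the analysis plan does not use it.

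Recruitment Procedures names three jails and surveys at "three different times: pre-exposure, after 6 months, and after 12 months from the beginning of the TEC". The Statistical Analysis Plan makes the 6-month survey scores the primary outcome, so referrals are a downstream outcome in a feasibility study meant to estimate effect sizes.

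**The concern.** To associate referral numbers with score changes, the referral numbers have to vary over something. The surveys are anonymous, and the documents describe no link between an individual officer's survey and that officer's referrals. The variation therefore has to come from time, from jail, or from both. Across either, the number of detainees who could be referred may differ.

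A raw count then mixes two things: how readily officers refer, which the campaign is meant to change, and how many detainees are in front of them, which it is not. A larger jail, or a fuller period, yields more referrals at the same officer behaviour. This referral association is the only stated hypothesis and the only step from officers' survey scores to detection. If its effect size carries a census change inside it, the later multi-site trial would be planned on a number that does not describe officer behaviour.

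**Working it through.** **The plan's own figure.** The one design figure is the number of surveys: 3 time points x 180 = 540, which reproduces. It concerns surveys only. No baseline or expected referral figure is stated, so there is nothing to reproduce on referrals.

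**Inputs.** The outcome (a count), the three jails and the three time points come from the documents. The two quantities below are assumptions, because the documents give neither:

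- r = true ratio of the referral rate, later period to earlier period (r = 1 means no change in officer behaviour);
- c = ratio of detainee census, later period to earlier period.

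**Formula.** If referrals scale with the number of detainees and the counting windows are equally long, count = rate x census. So

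- ratio of counts = r x c;
- ratio of rates = (r x c) / c = r.

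**Results.**

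| r (assumed) | c (assumed) | Ratio of counts | Ratio of rates |
|---|---|---|---|
| 1.00 | 0.80 | 0.80 | 1.00 |
| 1.00 | 1.20 | 1.20 | 1.00 |
| 1.25 | 0.80 | 1.00 | 1.25 |
| 1.50 | 0.70 | 1.05 | 1.50 |
| 2.00 | 0.80 | 1.60 | 2.00 |

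The first two rows show a campaign with no effect appearing to harm or to help. The third shows a true 25% rise disappearing. The fourth shows a true 50% rise reduced to 5%.

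**Census fall that exactly cancels a true rise.** Set r x c = 1. The fall is 1 - 1/r:

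- r = 1.10: 1 - 1/1.10 = 9.1%
- r = 1.25: 1 - 1/1.25 = 20%
- r = 1.50: 1 - 1/1.50 = 33.3%
- r = 2.00: 1 - 1/2.00 = 50%

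The smaller the true effect, the smaller the census change needed to erase it. The same formula applies between jails if c is read as the ratio of two jails' censuses: with equal rates (r = 1), the ratio of counts is simply the ratio of their sizes.

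Nothing here depends on which referrals are counted. It holds equally if only officer referrals of newly detected detainees enter the count.

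**The case against.** The strongest reply is about importance. The study is a survey of officers, its sample is 540 surveys, and its primary outcome is the 6-month scores. It disclaims significance testing. The survey-score effect sizes are untouched by this point, and the plan sets out no period-by-period or jail-by-jail comparison of counts. All of that is true, and it limits the point to the referral effect size. It does not remove it: a study whose purpose is estimation needs the estimated quantity to be defined, and any association over time or between jails inherits the census.

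It is also fair that the documents report no census change. The COVID-19 text in Recruitment Procedures concerns how surveys would be handed out and says nothing about detainee numbers. A census change during this study is a possibility, not a documented fact.

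A reader might go further and infer that the plan counts the wrong event: every referral to CHS from any source, including detainees already known to mental health services, so that new detections are diluted. Under an assumed 20% share of new detections, doubling them would raise the total only to 0.80 + 0.20 x 2 = 1.20. The documents do not support that reading. The paragraph's opening sentence already describes referrals made by officers, of detainees not detected before, and the later phrase reads naturally as shorthand for these. Nothing says that all CHS referrals will be counted, and the shares needed to size a dilution are nowhere given. The background does expect the campaign to generate referrals more broadly, "especially referrals of quietly psychotic young people who would have otherwise gone undetected and thus not referred to CHS", which leaves the boundary unclear. What remains on this side is missing operational detail, not a stated choice of a different event.

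**Conclusion.** The point holds for the denominator. The hypothesis uses a count where the plan's own account of the mechanism speaks of rates, and no population figure by jail or period is attached. In the illustration, a 20% census fall hides a 25% rise in the rate, and a 20% census rise imitates a 20% gain. These figures rest on assumed r and c and on referrals scaling with census. The actual size in this study cannot be computed from the documents.

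The consequence is a referral effect size confounded with census, for a downstream outcome, passed to the later trial. The primary outcome is not affected. The missing qualifiers on referrer and prior detection are a matter of clarification. The change should be made, but it does not undermine the study.

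**What to change.** 1. **Use a rate.** In Specific Aims and in the Statistical Analysis Plan, replace the number of referrals with referrals per 1,000 detainee-days, or per 1,000 admissions, for each jail and each period, including a pre-campaign period. State the counting windows and choose one denominator in advance. If a count model is used, log census (or log detainee-days) as an offset is equivalent.

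2. **Clarify the numerator.** Carry the paragraph's own qualifiers into the outcome wording: referrals by Correction Officers, of detainees not previously detected as having mental health concerns, where CHS referral records allow this. Say how prior detection is determined. Show total referrals alongside.

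**Cost.** Item 1 needs a wording change and aggregate census or admission counts by jail and period; no individual detainee data are needed for it. Item 2 costs more: referral records must be classified by source and prior detection, which this survey protocol does not describe, and the restriction leaves fewer events and a less precise estimate. If the records cannot support the classification, item 1 can be adopted alone, with the limitation stated.
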